9.7.3. Relative Administration Intensity

RAI will be calculated as the cumulative frequency of administration received over the expected number of administrations. Since response is needed to determine if switching to bi-weekly doses is appropriate and is not available in MDV, two schedule definitions will be used to estimate the expected number of administration to calculate RAI (Table 10. Dosing Schedule of Elranatamab during Follow-up Period for Patients Switching to

Q2W and Table 11. Dosing Schedule of Elranatamab during Follow-up Period for Patients staying on

QW Table 10. Dosing Schedule of Elranatamab during Follow-up Period for Patients Switching to

Q2W).

$$\text{RAI} = \frac{\text{Number of administrations received}}{\text{Number of expected administrations during the time period}}$$

a) Schedule 1¹

Assumption that all patients switch to bi-weekly doses (Q2W) after day 169 post-index.

Table 10. Dosing Schedule of Elranatamab during Follow-up Period for Patients Switching to Q2W

Follow-up Sub-Periods	Expected Administrations	Vial Size
Index date - Day 8	3 administrations	2 x 44mg/1.1mL 1 x 76mg/1.9mL
Day 9 - Day 168	1 administration per week	76mg/1.9mL
Day 169 – End of follow-up	1 administration every two weeks	76mg/1.9mL

Notes:

090177e1a4a71ff1\Approved\Approved On: 05-Nov-2025 14:15 (GMT)

¹ Adapted from dosing and administration guidance of the Japanese elranatamab label available at <https://labeling.pfizer.com/ShowLabeling.aspx?id=20462>

b) Schedule 2¹

Assumption that all patients continue with weekly doses (QW) after day 169 post-index.

Table 11. Dosing Schedule of Elranatamab during Follow-up Period for Patients staying on QW

Follow-up Sub-Periods	Expected Administrations	Vial Size
Index date - Day 8	3 administrations	2 x 44mg/1.1mL 1 x 76mg/1.9mL
Day 9 – End of follow-up	1 administration per week	76mg/1.9mL

Notes:

¹ Adapted from dosing and administration guidance of the Japanese elranatamab label available at <https://labeling.pfizer.com/ShowLabeling.aspx?id=20462>

Treatment exposure will be assessed across the different follow-up periods. End of follow-up is defined as the end of the hospital claim of the last elranatamab administration inclusive.

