SUD period: defined as the period between a patient's first 44mg/1.1mL vial of elranatamab and first 76mg/1.9mL vial of elranatamab, inclusive. See Section 9.3.1 and Annex 1 for more details. Within the SUD period, three sub-periods are identified:

- **Overall:** defined as the period between first 44mg/1.1mL vial and first 76mg/1.9mL vial of elranatamab.
- **First 44mg/1.1mL vial – Second 44mg/1.1mL vial:** defined as the period between the two 44mg/1.1mL vials of elranatamab, if second 44mg/1.1mL vial is administered.
- **Second 44mg/1.1mL vial – first 76mg/1.9mL vial:** defined as the period between the second 44mg/1.1mL vial and the first 76mg/1.9mL vial of elranatamab, if second 44mg/1.1mL vial is administered.

Follow-up period: defined as the period between the first hospital claim for elranatamab (index date) and the end of the hospital claim of the last elranatamab administration. Within this follow-up period, five sub-periods are identified (when sufficient follow-up time is available at the patient level). These sub-periods allow for reporting study endpoints across different phases of the follow-up period, and are based on expected dosing administrations and schedule of patients with switch to bi-weekly administrations from label guidance (see [Table 10. Dosing Schedule of Elranatamab during Follow-up Period for Patients Switching to](#)

[Q2W](#) and [Table 11. Dosing Schedule of Elranatamab during Follow-up Period for Patients staying on QW](#)):

- **Index date to day 8:** defined as the first 8 days post-index date, inclusive. Also defined as day 1 to day 8.
- **Day 9 to day 168:** defined as the period from day 9 to day 168 post-index date.
- **Day 169+:** defined as the period from day 169 post-index date to end of follow-up period.

- **Overall follow-up:** defined as the period from index date to end of follow-up period.

IVIG follow-up assessment period: defined as the 30-day window post index date. If a patient has fewer than 30 days of data available post to the index date, the assessment window will be equal to the maximum number of days available post to the index date.

CRS/ICANS follow-up assessment period: defined as the 14-day window post index date. If a patient has fewer than 14 days of data available post to the index date, the assessment window will be equal to the maximum number of days available post to the index date.

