9.3.1 Exposure Groups and Assessment Periods

[Table 1](#) outlines the variables to define exposure groups that will be used to identify patients and stratify analyses.

Table 1. Variables for Exposure

Variable	Role	Data Source	Operational Definition	
			Definition	Assessment Period(s)
Study population	Exposure	MDV	All patients with MM who have a hospital claim for elranatamab after March 26, 2024, and who meet the inclusion and exclusion criteria outlined in Sections 9.2.1 and 9.2.2.	Index date
SUD Exposure Group	Exposure	MDV	
Group A: Complete and timely SUD period
 
Patients in the study population with two 44mg/1.1mL vials (second 44mg/1.1mL vial is received 1 to 7 days after the first) and one subsequent 76mg/1.9mL vial between 1 to 7 days after second 44mg/1.1mL vial
 
Group B: Complete but not timely SUD period
 
Patients in the study population with two 44mg/1.1mL vials and one subsequent 76mg/1.9mL vial after the second 44mg/1.1mL vial, with one or both intervals between doses ranging from 8 to 14 days.
 
Group C: Alternative SUD period
 
 • Only one 44mg/1.1mL vial: patients in the study population with only one 44mg/1.1mL vial prior to receiving a 76mg/1.9mL vial • More than two 44mg/1.1mL vials: patients in the study population with more than 	SUD period

090177e1a4a71ff1\Approved\Approved On: 05-Nov-2025 14:15 (GMT)

Variable	Role	Data Source	Operational Definition	
			Definition	Assessment Period(s)
			
two 44mg/1.1mL vials prior to receiving a 76mg/1.9mL vial
 
 Extremely untimely: patients in the study population with more than 14 days between the first and second 44mg/1.1mL vial or between the second 44mg/1.1mL vial and the first 76mg/1.9mL vial 
Note that patients who received only 44mg/1.1mL vials or only 76mg/1.9mL vials are not classified under any SUD exposure group but will remain part of the study population.
	

Figure 2 illustrates possible elranatamab administration scenarios for each SUD group. These examples are not exhaustive and do not represent all potential administration schedules.

090177e1a4a71ff1\Approved\Approved On: 05-Nov-2025 14:15 (GMT)

Figure 2. SUD Periods Administration Schedule

[figure not shown]

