Antifungals	Baseline characteristics	MDV	Health claim code for antifungal medications (Yes/No)	14 days prior index date 365 days prior index date

Abbreviations: ADL: Activity of Daily Living; CAR-T: chimeric antigen receptor T-cell therapy; CCI: Charlson Comorbidity Index; cm: centimeter; IMiDs: immunomodulatory agents; IP: inpatient; IVIG: intravenous immunoglobulin; lb: pound; OP: outpatient; PI: proteasome inhibitors; SCT: stem cell transplant.

Table 4. Variables for Outcomes (Objective 2 - Treatment Administration, Dosing and Timing)

Variable	Role	Data Source	Operational Definition	
			Definition	Assessment Period(s)
44mg/1.1mL vial and 76mg/1.9mL vial [Summary statistic]	Outcome	MDV	Number of health claims for elranatamab per patient in the following categories: 
 ● 44mg/1.1mL vial ● 76mg/1.9mL vial 	SUD period

090177e1a4a71ff1\Approved\Approved On: 05-Nov-2025 14:15 (GMT)

Variable	Role	Data Source	Operational Definition	
			Definition	Assessment Period(s)
			Total number of health claims for elranatamab in the following categories: 
 • 44mg/1.1mL vial • 76mg/1.9mL vial 	Follow-up period
Time between first and second 44mg/1.1mL vials	Outcome	MDV	Days between claims for the first and second 44mg/1.1mL vial of elranatamab (continuous) Patients with <2 44mg/1.1mL vials are not included.	SUD period
Time between first 44mg/1.1mL vial and first 76mg/1.9mL vial	Outcome	MDV	Days between claims for the first 44mg/1.1mL vial and first 76mg/1.9mL vial of elranatamab (continuous)	SUD period
Time between second 44mg/1.1mL vial and first 76mg/1.9mL vial	Outcome	MDV	Days between claims for the second 44mg/1.1mL vial and first 76mg/1.9mL vial of elranatamab (continuous) Patients with <2 44mg/1.1mL vials are not included	SUD period
Time between elranatamab claims, patient level	Outcome	MDV	For patients with at least 2 elranatamab claims, the mean number of days between claims for elranatamab per patient will be reported	Follow-up period
Time between elranatamab claims, claim level	Outcome	MDV	For patients with at least 2 elranatamab claims, the mean number of days between claims for elranatamab will be reported alongside the number of intervals	Follow-up period

090177e1a4a71ff1\Approved\Approved On: 05-Nov-2025 14:15 (GMT)

Variable	Role	Data Source	Operational Definition	
			Definition	Assessment Period(s)
			between administrations in a given time period.	

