Duration of treatment, patient level	Outcome	MDV	Days between first and last treatment administration for elranatamab (continuous)	Follow-up period
Duration of treatment, claim level	Outcome	MDV	Total calendar duration of elranatamb observation in days, and the date of the first observed elrantatamab claim	Follow-up period
Only 44mg/1.1mL vials [Summary statistic]	Outcome	MDV	Number of patients with only 44mg/1.1mL vials during the time period (yes/no)	Follow-up period
Only 76mg/1.9mL vials [Summary statistic]	Outcome	MDV	Number of patients with only 76mg/1.9mL vials during the time period (yes/no)	Follow-up period
Relative Administration Intensity (RAI) [Summary statistic]	Outcome	MDV	Ratio of the elranatamab administrations received divided by the expected number of administrations according to the Japan elranatamab label See Section 9.7.4 for more details	Follow-up period

Abbreviations: mL: millilitre; mg: milligram; RAI: Relative Administration Intensity; SUD: step-up dosing.

Table 5. Variables for Outcomes (Objective 3 – HCRU and Costs)

090177e1a4a71ff1\Approved\Approved On: 05-Nov-2025 14:15 (GMT)

Variable	Role	Data Source	Operational Definition	
			Definition	Assessment Period(s)
IP claim [Summary statistic]	Outcome	MDV	Number of patients with ≥ 1 all-cause IP claim (yes/no)	HCRU baseline period SUD period Follow-up period (overall only)
			Number of all-cause IP claims PPPM. Reported for all patients and for patients with ≥ 1 all-cause IP claim.	HCRU baseline period Follow-up period (overall only)
			Number of all-cause IP claims PPPD. Reported for all patients and for patients with ≥ 1 all-cause IP claim.	SUD period
OP claim [Summary statistic]	Outcome	MDV	Number of patients with ≥ 1 all-cause OP claim (yes/no)	HCRU baseline period SUD period Follow-up period (overall only)
			Number of all-cause OP claims PPPM. Reported for all patients and for patients with ≥ 1 all-cause OP claim.	HCRU baseline period Follow-up period (overall only)
			Number of all-cause OP claims PPPD. Reported for all patients and for patients with ≥ 1 all-cause OP claim.	SUD period

090177e1a4a71ff1\Approved\Approved On: 05-Nov-2025 14:15 (GMT)

Variable	Role	Data Source	Operational Definition	
			Definition	Assessment Period(s)
ED claim [Summary statistic]	Outcome	MDV	Number of patients with ≥ 1 all-cause ED claim (yes/no)	HCRU baseline period SUD period Follow-up period (overall only)

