9.9. Limitations of the Research Methods

This study is subject to limitations, described below:

- The MDV database follows patients' medical journey through the same facility, not between facilities – as such there is visibility only on prior diagnoses received within the same facility. There may be a loss in data continuity due to hospital transfers, however, patients in Japan tend to be treated in the same centers therefore this may be minimal.
- Measures of MM disease severity, such as ISS stage, M-protein level, and cytogenetic risk are not available in MDV. This limits the extent to which patients' MM can be characterized.
- This study will use a secondary data source. Because of the secondary data source, common limitations apply to this study, including:
 - Data may not be complete or accurate due to potential errors in coding or record-keeping at the point of the healthcare provider.
 - Lags in data availability can lead to inaccuracies in timing of reported information. This can particularly impact estimates over short periods of time (e.g., HCRU on index date).
 - Missing data cannot confirm the absence of a condition or value in a patient's medical history; only that it was not documented.
 - The internal process of obtaining and cleaning data is not fully known by scientists using RW databases, as such the internal validity of RWD remains largely unknown to scientists working with the data (19). Although there are concerns about the validity of RWD, the MDV database still has been used for a large number of peer-reviewed publications (14).
 - The lack of granularity of certain variables can limit the research that can be done; for example, granularity of grade of infection is often not available.
 - Clinical trials have close monitoring and prospective data collection, which RWD lacks. This means that the description of AEs in RW patients is expected to be less precise. Additionally, estimates of incidence and prevalence of safety events are likely to be underestimated compared to clinical trials or prospective studies where timing of assessments can be controlled. However, RWD can be useful to describe incidences of AEs in a larger and more heterogenous samples (20).
- This study population consists Japanese patients treated with elranatamab in Japan; however, the data does not cover all patients in Japan. As such, results may not fully represent the broader experience of patients receiving elranatamab both within Japan and internationally.

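### RAI expects three administrations by day 8 from every patient, which is not reconciled with the step-up timing classes and biases RAI downward where step-up was given at another facility

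*Protocol*

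**What the plan says.** Relative administration intensity (RAI) is an Objective 2 variable, and Objective 2 is primary. In Section 9.7.3, "RAI will be calculated as the cumulative frequency of administration received over the expected number of administrations". Table 4 ties the denominator to the "expected number of administrations according to the Japan elranatamab label".

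Tables 10 and 11 both expect "3 administrations" from index date to day 8, made up of two 44mg vials and one 76mg vial. From day 9 both expect "1 administration per week"; they differ only from day 169. Section 9.2 describes the first sub-period as "defined as the first 8 days post-index date, inclusive. Also defined as day 1 to day 8". Table 2 reports Objective 2 follow-up outcomes in the whole study population.

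The step-up classes are in Table 1 (Section 9.3.1) and Table 12 (Annex 2). Group A, complete and timely, allows 1 to 7 days between the two 44mg vials and then "one subsequent 76mg/1.9mL vial between 1 to 7 days after second 44mg/1.1mL vial". The note in Table 1 keeps patients with only 76mg vials in the study population, outside any step-up group. Section 9.9 says that the database follows a patient's "medical journey through the same facility, not between facilities".

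**The concern.** Two parts of the protocol measure the same step-up against different clocks. RAI allows 8 days for three administrations; Group A allows up to day 15. Nothing says whether this difference is intended. One report could therefore describe a patient as complete and timely and also give that patient an intensity of two thirds over the first 8 days.

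The second problem concerns patients whose records contain no 44mg vial. Some may have had no step-up. Others may have had it at a hospital whose records are not linked, so that their index date is really a continuation dose. The RAI rule treats both alike. For the second kind, the denominator counts doses that were given but cannot be seen, and the ratio is wrong rather than merely low.

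Section 9.7.5 repeats Objective 2 in low-weight patients, so both problems carry into that subgroup.

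**Working it through.** **Inputs.** Three expected administrations in days 1 to 8, then one per week from day 9 (Tables 10 and 11). Group A intervals of 1 to 7 and 1 to 7 days (Tables 1 and 12). Follow-up ends with the claim of the last administration (Section 9.7.3); I assume that this claim closes on the dosing day.

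**The plan's figure.** 2 × 44mg + 1 × 76mg = 3 expected administrations, as stated.

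**Days 1 to 8, Group A.** With whole-day intervals i and j, doses fall on days 1, 1 + i and 1 + i + j. Since i is at most 7, the second dose is always in by day 8. The third is in only if i + j ≤ 7. The latest possible third dose is on day 1 + 7 + 7 = 15. Of the 7 × 7 = 49 interval patterns:
- 21 have i + j ≤ 7 and give 3/3 = 1.00;
- 28 have i + j > 7 and give 2/3 = 0.67.

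**Overall, up to day 168.** Expected = 3 + (L − 8)/7 for a last dose on day L. The values of L below give whole weeks, so no rounding rule is involved. A patient dosed on days 1, 8 and 15 and weekly after that has received 1 + (L − 1)/7 doses. A patient dosed on days 1, 4 and 8 and weekly after that has received 3 + (L − 8)/7.

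| Last dose (day) | Expected | Received, days 1/8/15 | RAI | Received, days 1/4/8 | RAI |
|---|---|---|---|---|---|
| 15 | 4 | 3 | 0.75 | 4 | 1.00 |
| 29 | 6 | 5 | 0.83 | 6 | 1.00 |
| 85 | 14 | 13 | 0.93 | 14 | 1.00 |
| 162 | 25 | 24 | 0.96 | 25 | 1.00 |

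The shortfall in the 1/8/15 pattern is one dose throughout. For patterns in between, the overall result depends on how part-weeks are counted. With doses on days 1, 5 and 9 and follow-up ending on day 9, overall RAI is 0.95, 1.00 or 0.75 with part-weeks taken as fractions, rounded down or rounded up. The value for days 1 to 8 is 0.67 in each case.

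**Only 76mg vials.** Weekly dosing from index puts doses on days 1 and 8, so RAI in days 1 to 8 is 2/3 = 0.67. The overall values equal those of the 1/8/15 pattern, because the dosing days are the same. A patient with a single claim scores 1/3 = 0.33, provided that the three expected doses are not cut back at the end of follow-up.

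**The case against.** The strongest reply is that these are two different measures. RAI is referenced to the label by definition, while Group A is a tolerance band used to stratify step-up outcomes. A patient can be within tolerance and behind the reference schedule, and Table 2 does not plan RAI by step-up group. For a patient who truly had no step-up, a value below 1 is what a label-referenced ratio should show. This stands: the passages are unreconciled, and neither contains an arithmetic error. It does not answer the case of step-up given but not recorded.

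The protocol also discloses the single-facility limit, suggests that the loss from transfers may be minimal, and counts patients with only 76mg vials as a separate outcome in Table 4. That makes the group visible but does not remove it from the RAI. No figure in the document shows how large it is.

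The overall deficit also fades. Section 9.7.1 rounds means and medians to one decimal, so 0.96 would print as 1.0. The effect lies in days 1 to 8 and in short follow-up.

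A reader might infer more than the document supports:
- That patients on schedule cannot score 1. Any patient with exactly three administrations by day 8 scores 1 in that window.
- That 28/49 is a share of Group A patients. It counts interval patterns; no interval distribution is given.
- That days 9 to 168, being 160 days, by themselves make RAI wrong. Twenty-two weekly doses against 160/7 = 22.86 give 0.96 with fractional weeks but 1.00 with weeks rounded down. Section 9.7.3 does not fix the rule, and the SAP may.
- That continuing users are known to be mixed with initiators. This is possible, not shown.

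**Conclusion.** The point holds in two parts. First, the three-dose expectation by day 8 and the Group A limit of day 15 are not reconciled, so a patient classed as complete and timely can score 0.67 in days 1 to 8. In the 1/8/15 pattern that patient stays one dose short overall, from 0.75 at day 15 to 0.96 at day 162. It would be too strong to call this a contradiction, because the difference may be deliberate; the protocol does not say so.

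Second, patients with only 76mg vials are divided by the same three doses (0.67 on weekly dosing, 0.33 with one claim), although the data cannot separate omitted step-up from step-up given elsewhere. For the latter, RAI is biased downward. The size in the whole cohort depends on how many such patients there are, which the document does not give.

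The figures assume strictly weekly dosing after the pattern shown and a last claim that closes on the dosing day. The analysis is descriptive, so no test is affected, but RAI belongs to a primary objective and both rules are fixed in the protocol.

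**What to change.** 1. Reconcile Tables 1 and 12 with Tables 10 and 11 on the time to the first 76mg vial, or state in Section 9.7.3 that the timeliness classes and the RAI reference schedule differ by design. This review takes no view on which timing is right.
2. Report RAI separately for patients whose first elranatamab claim is a 76mg vial. This covers the patients with only 76mg vials and any who have a 44mg vial later.
3. Leave these patients out of the index-to-day-8 RAI and its three-dose denominator, and state what denominator their overall RAI uses.

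The exclusion should apply to RAI only, since Objectives 3, 4 and 6 use the same follow-up periods. The cost is a few sentences of protocol and SAP text, a change to the programming of one variable, fewer patients in the early RAI sub-period and one extra table row.

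### Section 9.7.3 gives expected administrations after day 8 only as rates; applied to sub-period length, these can push the RAI from day 169 above 1 for a patient dosed exactly on schedule

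*Protocol*

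**What the plan says.** Section 9.7.3 defines the measure: "RAI will be calculated as the cumulative frequency of administration received over the expected number of administrations". The denominator relates to the time period in question, and the section adds: "Treatment exposure will be assessed across the different follow-up periods". Table 2 in section 9.3.1 lists the sub-periods in which Objective 2, a primary objective, is reported.

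Section 9.2 sets the sub-periods:
- The first is "defined as the first 8 days post-index date, inclusive. Also defined as day 1 to day 8".
- The second is "defined as the period from day 9 to day 168 post-index date".
- The last is "defined as the period from day 169 post-index date to end of follow-up period".

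Table 10 gives a count for the first ("3 administrations") but only a rate for the second ("1 administration per week"). From day 169 it gives one administration per two weeks under Schedule 1. Under Schedule 2 (Table 11) the weekly rate continues.

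The text above Table 10 reads: "Assumption that all patients switch to bi-weekly doses (Q2W) after day 169 post-index". Table 10 itself applies the two-weekly rate from day 169, so the two disagree about that day.

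Sections 9.2 and 9.7.3 end follow-up at the end of the claim that contains the last administration.

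**The concern.** A patient who receives every scheduled administration should have an RAI of 1 in every sub-period. A rate multiplied by elapsed time does not guarantee this when a window starts and ends on dose days, because such a window holds one dose more than its length divided by the interval. The last sub-period has this form whenever day 169 is a dose day and the last claim is a same-day claim.

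The inflated values would sit in a primary-objective variable. Section 9.3.1 admits to a sub-period any patient with at least one elranatamab claim in it, or whose follow-up ends in it, so a patient last dosed on day 169 enters with a one-day denominator. Section 9.7.1 reports mean, SD and maximum, which are sensitive to such values. The cohort is small (128 patients with a claim at the February 2025 cut, section 9.5). The low-weight subgroup repeats Objective 2 (section 9.7.5), and no sensitivity analysis is planned (section 9.7.6).

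**Working it through.** The protocol states no RAI value, so there is no figure to reproduce. The check takes a patient dosed exactly on schedule and asks whether each sub-period returns 1.

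**Inputs from the protocol.** Index date = day 1 and the sub-period limits (section 9.2); three administrations in days 1-8, then one per 7 days, then one per 14 days from day 169 under Schedule 1 or one per 7 days under Schedule 2 (Tables 10 and 11).

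**Assumptions.** Third administration on day 8; last claim ends on the day of the last dose; expected administrations = sub-period length divided by the interval (pro rata). Each is varied below.

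**Dose days.** Weekly doses after day 8 fall on 8 + 7j: days 15, 22, ..., 162, 169, since 8 + 7 × 23 = 169. Day 169 is a dose day and the first day of the last sub-period.

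**Days 9-168.** Length 168 − 9 + 1 = 160 days; expected 160/7 = 22.857; received (162 − 15)/7 + 1 = 22. RAI = 22/22.857 = 0.9625. Rounding the denominator down gives 22/22 = 1.00; rounding up or to nearest gives 22/23 = 0.957.

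**Day 169 onward, Schedule 1.** With m two-weekly doses after day 169, received = m + 1, length = 14m + 1 days, expected = (14m + 1)/14, so RAI = (m + 1)/(m + 1/14).

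| Last dose | m | Pro rata | Floor or nearest integer, (m+1)/m | Ceiling |
|---|---|---|---|---|
| day 169 | 0 | 14.0 | 1/0, undefined | 1.00 |
| day 183 | 1 | 1.87 | 2.00 | 1.00 |
| day 197 | 2 | 1.45 | 1.50 | 1.00 |
| day 253 (12 weeks) | 6 | 1.15 | 1.17 | 1.00 |
| day 337 (24 weeks) | 12 | 1.08 | 1.08 | 1.00 |
| day 533 (one year) | 26 | 1.04 | 1.04 | 1.00 |

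**Day 169 onward, Schedule 2.** With n further weekly doses, RAI = (n + 1)/(n + 1/7): 7.0 at day 169, 1.40 at day 183 (n = 2), 1.07 at 12 weeks (n = 12), 1.02 at one year (n = 52).

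**Last claim ending e days after the last dose (Schedule 1).** RAI = 14(m + 1)/(14m + 1 + e). For e = 7: 1.75, 1.27, 1.07 and 1.02 at m = 0, 1, 6 and 26. For e = 13: 1.00 throughout.

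**First dose of the last sub-period d days after day 169, as when the third dose precedes day 8 (Schedule 1).** RAI = 14(m + 1)/(14m + 1 + d). For d = 6: 2.00, 1.33 and 1.08 at m = 0, 1 and 6. For d = 13 it is 1.00: for example, third dose on day 7, a weekly dose on day 168 and the next on day 182. With the third dose on days 3-7, days 9-168 hold 23 doses and score 23/22.857 = 1.006.

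**Overall RAI, Schedule 1.** (3 + 22 + m + 1)/(3 + 160/7 + (14m + 1)/14). At m = 0 this is 26/25.929 = 1.003, and it falls as m grows. Under Schedule 2 it is 1.000. The two sub-period errors cancel.

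**Counting scheduled dates instead.** Expected = 22 in days 9-168 and m + 1 from day 169, so RAI = 1.00 in both for every m.

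**The case against.** The strongest reply is that section 9.7.3 never says expected administrations equal length divided by interval. Tables 10 and 11 are titled as dosing schedules; counting scheduled dates is an equally natural reading and gives 1.00 in both sub-periods. Section 9.7 leaves detailed methodology to the SAP, which may settle this. That stands as a limit: the inflation follows from one reading of the text. But beyond day 8 the protocol offers only a rate, and three of the four obvious ways of using it (pro rata, floor, nearest integer) give a wrong value from day 169. Rounding up does not, and its 0.957 in days 9-168 prints as 1.0 under the one-decimal rule of section 9.7.1, but nothing in the protocol selects it.

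The day-8 anchor is also inferred, and the dose pattern around day 169 matters: one pattern with the third dose on day 7 gives exactly 1.00. This stands too.

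A reader might infer three stronger things that the documents do not support:
- **A shortfall in the weekly phase.** The 0.9625 rests on the same assumptions and also prints as 1.0.
- **A typical RAI of about 2 after day 169.** If last doses are spread evenly over m = 0 to 12 (an assumption), the Schedule 1 mean is 2.21. That rests on the single 14.0: without it the mean is 1.23, and the median of all 13 values is 1.15. Section 9.7.1 also reports median and IQR.
- **A guaranteed apparent improvement in adherence.** The study is descriptive, the excess fades with longer treatment, and it disappears under date counting.

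**Conclusion.** The point holds in a limited form. The protocol's rates, applied to sub-period length, overstate RAI from day 169 for an on-schedule patient whose third dose is on day 8 and whose last claim is a same-day claim. The overstatement is large only for short tails and is 4% at one year. It is smaller, or absent, when the last claim runs on or the dose pattern shifts. It concerns the sub-period RAI of patients treated past day 168; the days 9-168 value and the overall RAI are essentially unaffected.

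The size depends on the inferred day-8 anchor and a pro-rata, floor or nearest-integer denominator. Independent of both is the disagreement between the Schedule 1 sentence and Table 10 about day 169, which is a plain inconsistency in the text. The change is worth making because the variable serves a primary objective, patients with one claim in the window are scored, and the remedy is cheap.

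**What to change.** In section 9.7.3:
- Define expected administrations in each sub-period as the number of scheduled dose dates implied by Tables 10 and 11 that fall within the patient's observed part of that sub-period.
- State the anchor date from which those dates are counted.
- State that a sub-period with no expected administration is not scored.
- Reconcile the Schedule 1 sentence with the last row of Table 10 about day 169. Which reading is intended is for the sponsor to say.

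Two simpler changes are not equivalent and are not recommended. A fixed count of 22 for days 9-168 would score an on-schedule patient with the third dose on day 7 at 23/22 = 1.045. Moving the cut to day 169/170 would score such a patient, dosed on days 168 and 182, at 1/(13/14) = 1.08 for days 170-182, where the present cut gives 1.00.

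The cost is a few sentences in section 9.7.3, matching text in the SAP and a small programming change. No new data are needed.
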